We will also use additional measurements of medication adherence to validate the findings from the CleverCap™ Lite dispenser. We will do blood draws at baseline, 3 and 6 months to measure CD4 and viral load data on each study participant; alternatively, participants will be given the option of providing recent lab results of their CD4 and viral load data. The blood draw at baseline will also be tested for genotyping, GSA chip and qPCR, Hormone blood levels (Estrogen and FSH), and cytokine blood levels (IL-1 β , IL-2, IL-4, IL-6, IL-8, IL-10, IL-13, TNF α , and CRP). The genotyping with GSA chip and qPCR, cytokine blood level and CRP, and hormone blood tests will only be collected once during the course of the study, at Baseline or at the 6-month follow-up if not completed at Baseline. The genotyping, GSA chip and qPCR will be performed by the Feinstein Institute for Medical Research at Northwell Health. We will also ask participants to complete the Center for Adherence Support Evaluation (CASE) Adherence Index, a simple composite measure of self-reported antiretroviral therapy (ART) adherence⁸¹. The CASE Adherence Index consists of three unique adherence questions. Past research has shown that the CASE Adherence Index correlated strongly with the three-day self-reported adherence data ($p<0.001$) and was more strongly associated with HIV outcomes, including a 1-log decline in HIV RNA level (maximum OR=2.34; $p<0.05$), HIV RNA<400 copies/ml (maximum OR=2.33; $p<0.05$) and performed as well as the three-day self-report when predicting CD4 count status. The CASE Adherence Index is an easy to administer instrument that provides an alternative method for assessing ART adherence in clinical settings. Items are scored such that higher values indicate better adherence, and the maximum total score is 16. Scores of 11 or higher on this index indicate good adherence (Cronbach's $\alpha=0.79$)⁸⁶.

Our primary outcome is ART adherence. The CleverCap™ Lite dispenser is our objective measure of ART adherence and the CASE Adherence index as a subjective measure. We are including the subjective measure since there is potential bias in that participants' in the control group may not use the device or may not use the device for the entire study period.

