We will assess for contamination between the study groups at the end of the trial by asking control group participants whether they had used any HIV or medication related apps in the past 6 months. In addition, participants will return at 3 and 6 months to complete the remainder of the measures listed in Table 3 and included in the Appendix. We will also collect data on app use through automated log files so there will not be response burden associated with this measure.

Secondary Outcome Measures: Our measures are listed in Table 3 and included in the Appendix.

D.9. Data Analysis.

We will use intention-to-treat principles for the primary outcome analysis. Intention to treat implies all subjects are considered in analyses. The outcome variable y_{-i} will be the total number of times the CleverCap™ Lite dispenser is opened at day t (from day 1 to day 180) for person i , so y_{-i} follows binomial distribution with parameter of p_{-i} and n where p is probability of taking medication (adherence rate) and n is number of medications to take each day. We use a generalized linear mixed model (GLMM) with logit link function to analyze adherence rate. The basic form of the model is: $\log(p_{-i}/(1-p_{-i})) = \beta_0 + \beta_1 t + \beta_2 t \times \text{INT} + \mu_{-i}$. In the model, μ_{-i} is person level random effect and follows normal distribution. This model is also called individual growth model. Independent variable INT is an indicator for intervention group (INT=1 for the intervention group and INT=0 for the control group). Regression parameter β_1 is change in adherence rate for the control group and β_2 is the difference in change in adherence rate between the intervention group and the control group.

This model can include personal level factors as covariates so we can test for potential confounding by covariates (i.e., age, gender, and health literacy) in this model and inspecting for changes in the point estimate of the relation between study group and adherence.

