We will use GLMM for analyzing secondary outcomes. In our analysis of the surveys related to the SDT framework, the variable time (t) will be at 3 time points (baseline, 3 month, and 6 month) and the link function will be identified for continuous outcomes. In the analysis of app use, the unit of analysis will be at daily level for each participant, and system use will be analyzed using a GMMM with log link function (Poisson model). For the analysis of CD4 and viral load, we will analyze difference-in-difference using GLMM with identity or log link function when these variables are treated as continuous outcomes. Viral load will also be treated as a binary outcome (detectable vs. undetectable) and analyses of viral suppression will use the GLMM with logit link. In a secondary “as treated” analyses, missing adherence and viral load data will be ignored. The genotype analysis will be run by the Feinstein Institute for Medical Research at Northwell Health. Finally, we will assess the relationship between adherence (independent variable) and virologic suppression (dependent variable) using GLMM logistic regression and including missing viral load as detectable. This model will include personal level factors as covariates so we can test for potential confounding by covariates (i.e., age, gender, and health literacy) in this model and inspecting for changes in the point estimate of the relation between study group and adherence.

E. Aim 2b: Assess the acceptability of the CleverCap™ dispenser through In-depth interviews, which will focus on the individual experience of PLWH with the device.

E.1. Sample. At the 3-month follow-up visit, semi-structured in-depth interviews will take place with participants in the intervention group. These participants will be the same participants from the intervention study arm, if they choose to participate (N=100)

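### The CD4 and viral load model in D.9 is a difference-in-difference that does not name the collected baseline value as a covariate; read conventionally it gives up precision, by an amount that depends on a correlation the plan does not state

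*Combined protocol and SAP*

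**What the plan says.** Section D.9 of the combined protocol and SAP states "We will use GLMM for analyzing secondary outcomes". For the laboratory outcomes it continues: "For the analysis of CD4 and viral load, we will analyze difference-in-difference using GLMM with identity or log link function", with the limit "when these variables are treated as continuous outcomes". A second analysis follows: "Viral load will also be treated as a binary outcome (detectable vs. undetectable) and analyses of viral suppression will use the GLMM with logit link".

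Section D.8 provides the baseline: "We will do blood draws at baseline, 3 and 6 months to measure CD4 and viral load data on each study participant". As an alternative to the draw, "participants will be given the option of providing recent lab results of their CD4 and viral load data"; no time window is attached to such results.

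The covariates named in D.9 are age, gender and health literacy. Baseline CD4 and baseline viral load are not named.

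No formula is written for the CD4 or viral load model. The only GLMM written out is the one for daily adherence: logit(p) = β0 + β1·t + β2·t×INT + person effect. It has no INT main effect, and the text says that β2 "is the difference in change in adherence rate between the intervention group and the control group".

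Table 3 places CD4 and viral load under the primary outcome block but names the dispenser as the primary measure. D.8 uses the blood results to check the dispenser findings.

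**The concern.** In its usual form, a difference-in-difference gives each arm its own baseline mean and compares the changes. Allocation here is random (D.6), so any difference between the arms at baseline is chance. Subtracting each arm's own baseline fixes the baseline coefficient at 1, whereas the data would support a value near r when baseline and follow-up variances are equal. The excess carries chance imbalance and baseline noise into the treatment contrast. If recent laboratory results supplied by participants, with no window, add noise to the baseline, a change score takes that noise in full.

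What is at stake is the precision of a supporting check. D.8 admits that control participants may not use the dispenser, or may stop using it. The other adherence check, the CASE index, is self-report. Among the adherence-related measures, CD4 and viral load are the ones that depend on neither bottle handling nor self-report. No power is stated for them, so there is no known margin from which to spend precision.

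**Working it through.** **Inputs from the documents.** 200 participants and 25% attrition in both arms (D.4), hence 200 × 0.75 = 150 completers; 1:1 allocation (D.6), hence 75 per arm. Two-sided alpha 0.05 (D.4). Visits at baseline, 3 and 6 months (D.8).

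**Inputs not in the documents.** The correlation r and the SD of CD4 or viral load. r is assumed over a range; the SD σ cancels from the comparison.

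**The plan's own figure.** There is none to reproduce. The powers in D.4 (90.7% and 88.6%) concern dispenser adherence only.

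**One follow-up visit, identity link, equal variance σ² at both visits, n per arm.**

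- Difference-in-difference: Var = (2σ²/n) × 2(1 − r)
- Baseline-adjusted: Var = (2σ²/n) × (1 − r²)
- Ratio, adjusted over difference-in-difference: (1 − r²) / [2(1 − r)] = (1 + r)/2
- Information lost: 1 − (1 + r)/2 = (1 − r)/2

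With n = 75 and σ = 1:

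| Assumed r | Var, difference-in-difference | Var, adjusted | Information lost | 150 completers worth | SE ratio |
|---|---|---|---|---|---|
| 0.3 | 0.03733 | 0.02427 | 35% | 97.5 | 1.240 |
| 0.5 | 0.02667 | 0.02000 | 25% | 112.5 | 1.155 |
| 0.7 | 0.01600 | 0.01360 | 15% | 127.5 | 1.085 |
| 0.8 | 0.01067 | 0.00960 | 10% | 135 | 1.054 |
| 0.9 | 0.00533 | 0.00507 | 5% | 142.5 | 1.026 |

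Simulation with 75 per arm and 20,000 runs gave losses of 34.6%, 24.7% and 9.8% at r = 0.3, 0.5 and 0.8, in agreement with the formula.

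Ignoring baseline altogether has variance factor 1. Since 2(1 − r) > 1 when r < 0.5, a difference-in-difference is then worse than not using baseline at all.

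In terms of power: where the adjusted analysis would have 80%, the difference-in-difference has Φ(2.802 × √[(1 + r)/2] − 1.960), which is 61.7%, 67.9%, 75.7% and 78.0% at r = 0.3, 0.5, 0.8 and 0.9.

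**Three visits, compound symmetry, exact generalised least squares, 6-month contrast.**

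- Categorical visit with an arm main effect: the losses are those in the table (35%, 25%, 15%, 10%, 5%).
- Categorical visit without an arm main effect (common baseline): the variance equals the adjusted analysis exactly. At r = 0.5 it is 0.0200, against 0.0267 with the arm main effect. The loss is zero.
- Linear time without an arm main effect, the literal form of the primary model: 0.0194 at r = 0.5. Nothing is lost, but this relies on the trend being linear.

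If the target were the mean of the two follow-ups, the loss of the conventional form would be 2(1 − r)/3: 47% at r = 0.3 and 13% at r = 0.8.

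**The case against.** The strongest objection is that the plan may already avoid the problem. The only GLMM it writes out has a common intercept, and its interaction coefficient is described as a difference in change, which is difference-in-difference language for a common-baseline model. Reused for CD4 and viral load with categorical visit, it loses nothing against baseline adjustment. This stands as a possible reading. It does not settle the matter: that formula is written for daily adherence on the logit scale, D.9 does not carry it over, and the term used for the laboratory outcomes normally implies an arm-specific baseline. Two analysts could fit different models from this text and report different standard errors.

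Other limits also stand. The loss is one of precision; under randomisation a conventional difference-in-difference remains valid. The dispenser is the primary measure, and no power claim rests on the laboratory values.

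A reader might infer that the trial is throwing away 10% to 35% of its laboratory information. The documents do not support that as a fact: the range only restates an assumed r of 0.8 to 0.3, and the loss is 5% at r = 0.9. Nor can the percentage be attached to the log-link or binary analyses, for which the formula was not derived.

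A reader might also argue that viral load must be conditioned on because it is an entry criterion. That is weak: D.2 admits participants on low self-reported adherence or on viral load, so it is only one of two routes, and regression to the mean is expected equally in both randomised arms.

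**Conclusion.** The point holds as a matter of specification and precision. D.9 names a difference-in-difference for continuous CD4 and viral load, does not name the collected baseline value as a covariate, and does not write the model. Under the conventional reading, and for an identity-link outcome at one follow-up visit with equal variances, the analysis is less precise than baseline adjustment for any r below 1, by (1 − r)/2. Under the common-intercept reading with categorical visit, the loss is zero. Confidence is high in the method and moderate at best in the size, because r is unknown and the model form is not stated.

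This is not evidence of bias, and it does not affect the primary dispenser analysis. It should be corrected because the gain in precision is free under one reading and the clarification is needed under both.

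**What to change.** In D.9, replace the difference-in-difference wording for continuous CD4 and viral load with one of these two models, written out in full:

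- a repeated-measures model of the 3- and 6-month values with arm, categorical visit, arm by visit, and the participant's own baseline value as covariate; or
- a model of all three visits with categorical visit and arm by follow-up visit, constrained to one common baseline mean (no arm main effect).

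Name the 6-month arm difference as the reported contrast. For binary suppression, include baseline suppression status as a covariate.

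The cost is a change of SAP wording. It needs no new data, visits or participants.

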1) The Comprehensive Health Program at Columbia University/NewYork-Presbyterian Hospital provides primary care, HIV specialty care and care coordination services to over 2,000 PLWH. 95% of individuals are of either Black or Latino background and women represent half of the overall population. In addition, the program has 28 direct clinical providers, 8 social workers, and 10 additional care coordinators. Of note, [name] (Co-I) is an attending physician at the Clinic.

2) AIDS Service Center (ASC) is a community based organization for PLWH and persons at risk for HIV. ASC has more than 90 staff, 85 peer interns, and more than 1,800 clients who come for services each year. In addition, another 18,000 people are reached through the peer education and community outreach initiatives of ASC. Given our past experience and success in recruiting participants and using the recruitment strategies described above, we are confident that we will be able to recruit the number of participants needed to conduct the study within the study timeframe. See details in Section A.3.3. Preliminary Work.

STATISTICAL PROCEDURES

D.4. Power and Sample Size.

We will recruit 200 individuals and have greater than 80% power to detect a less than 10% difference in adherence to ART medications between the Wise App and the control group. We assume a 25% attrition rate by the end of trial for both arms. The power calculations are based on the analysis of main outcome, ART adherence. All calculations are based on 2-sided test with alpha at 0.05 level. Our calculations are based on the assumption that each person is on a once daily regimen and the adherence rate is $\leq 80\%$ at baseline.

Many of our participants will be on regimens that are two or three times per day which will provide greater power for our study since we have a greater number of measurements (e.g., 180 for once daily vs. 360 for twice daily regimen). To illustrate, if the adherence rate for the control group does not change, we will have 90.7% power to detect a 6% increase in ART adherence for the intervention group (e.g., from 80% to 86% at

Table 2. Comparison of Intervention vs. Control Group

	Intervention	Control
The Wise App • Medication reminder • Step Goal reminder	✓ ✓	✓
CleverCap™ Lite dispenser	✓	✓

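### In the secondary model of viral suppression on adherence, counting missing viral load as detectable is not reliably conservative and should be reported beside a second analysis (minor)

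*Combined protocol and SAP*

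**What the plan says.** The last model in D.9 regresses virologic suppression (dependent) on adherence (independent), "using GLMM logistic regression and including missing viral load as detectable". The covariates named are age, gender and health literacy. No reason is given for the coding, and no sensitivity analysis is attached to this model.

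Earlier in the same paragraph, D.9 announces a secondary 'as treated' analysis in which "missing adherence and viral load data will be ignored". That sentence comes before the adherence-suppression model and is not tied to it.

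Three other places bear on how much viral load could be missing, and in whom:

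- D.4: "We assume a 25% attrition rate by the end of trial for both arms".
- D.8 schedules viral load at baseline, 3 and 6 months. As an alternative to the blood draw, "participants will be given the option of providing recent lab results of their CD4 and viral load data".
- D.2 admits people with self-reported adherence of 80% or less, or a viral load over 400 copies/mL. Someone who enters on self-report alone may therefore be suppressed.

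**The concern.** Counting missing as failure is usually defended as cautious when two randomised arms are compared. Here the comparison runs along adherence, so the rule assigns outcome values along the exposure axis. How it moves the odds ratio depends on how missingness is spread over adherence levels and on how many of the missing are really suppressed. The plan settles neither.

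At stake is the reported strength of the adherence-suppression association. With a single stated coding, a reader could not tell whether that strength had been shrunk, inflated or left alone.

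**Working it through.** D.9 gives no odds ratio, power or missing rate for this model, so there is no figure of the plan to reproduce. The check is an exact two-group calculation.

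**Inputs**

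- Half the participants have low adherence and half high (assumed).
- True odds ratio 2.33. D.8 quotes this as a maximum odds ratio for the CASE index against HIV RNA below 400 copies/mL. It is used only as an illustrative size.
- Overall suppression 25, 50, 70 or 80% (assumed). The rationale section gives about 25% for people living with HIV in the US, which is a national figure and not one for this trial.
- 25% missing, taken from the D.4 attrition figure. That is attrition by the end of the trial, so it is an upper-end proxy for viral load missing over all visits. Half of it, 12.5%, is also shown (assumed).
- Within an adherence group, missingness does not depend on viral load (assumed for the first table).

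**Formula.** Let pL and pH be the true suppression probabilities at low and high adherence, and mL and mH the missing shares. Coding missing as detectable turns p into p(1 − m), so

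OR = odds[pH(1 − mH)] / odds[pL(1 − mL)], with odds(x) = x/(1 − x).

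**One case in full.** At 50% suppression, pL + pH = 1 and the true odds ratio is 2.33, so pL = 1/(1 + √2.33) = 0.3958 and pH = 0.6042.

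- With 25% missing in both groups, the coded rates are 0.75 × 0.3958 = 0.2969 and 0.75 × 0.6042 = 0.4531.
- The odds are 0.4222 and 0.8286, and the ratio is 1.96.

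**All cases (true odds ratio 2.33, missing coded as detectable)**

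| Missing, low / high adherence | 25% suppressed | 50% | 70% | 80% |
|---|---|---|---|---|
| 25% / 25% | 2.19 | 1.96 | 1.69 | 1.51 |
| 12.5% / 12.5% | 2.25 | 2.12 | 1.91 | 1.74 |
| 35% / 15% | 3.05 | 3.05 | 3.05 | 3.05 |
| 15% / 35% | 1.57 | 1.28 | 0.96 | 0.77 |

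**Where the direction turns.** The gap in missingness (low minus high adherence) at which the coded odds ratio returns to 2.33 is 3.9/7.9/11.0/12.6 percentage points with 25% missing overall, and 2.3/4.6/6.4/7.3 points with 12.5%. Below that gap the bias is toward 1; above it the bias is upward.

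**When there is no bias.** If every missing value is truly detectable, the coding assigns the right value and the odds ratio stays at 2.33. Records that drop out because adherence is also missing are not affected by the coding.

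**The same test for the alternative.** Suppose all missing values are truly detectable and only observed viral loads are fitted. The observed rate is then p/(1 − m). At 50% suppression:

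- 25/25% missing: 0.3958/0.75 = 0.5278 and 0.6042/0.75 = 0.8056, odds ratio 3.71.
- 35/15% missing: 0.3958/0.65 = 0.6089 and 0.6042/0.85 = 0.7108, odds ratio 1.58.

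In a halfway case, missing participants are suppressed at half the rate of observed participants in the same adherence group. The observed rate is then q = p/(1 − 0.5m) and the coded rate is q(1 − m). At 50% suppression, missing-as-detectable and observed-only give 2.09 and 2.70 at 25/25%, and 2.75 and 2.04 at 35/15%. Both are off, on opposite sides of 2.33.

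The calculation is marginal. It leaves out the covariates and the person-level random effect of the planned GLMM, so the sizes are indicative.

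**The case against.** The strongest reply is that D.9 already contains the comparison. The 'as treated' analysis ignores missing adherence and missing viral load, which are the two variables in this model. Read generously, it supplies the observed-data fit. This stands in part: one sentence of scope would close much of the gap. As written, though, the sentence is not tied to this model.

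A second reply is that 25% is too high, since viral load is collected at three visits and recent laboratory results are accepted. That also stands. The distortion is smaller at 12.5%, and it is small at 25% suppression with equal missingness (2.33 becomes 2.19 or 2.25).

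Some stronger readings are tempting, but the documents do not support them:

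- *The coding manufactures an association from nothing.* This is arithmetically possible, but the rationale section and D.8 both presuppose that adherence and suppression are linked. D.9 also states no hypothesis or significance level for this model. Distorted size is the realistic issue.
- *Observed viral loads give the correct answer and the planned coding is wrong.* The figures 3.71 and 1.58 for a true 2.33 rule that out. Which analysis is nearer the truth depends on the unknown state of the missing values.
- *D.8 shows which direction applies*, because control participants "may not use the device or may not use the device for the entire study period". That remark concerns recorded adherence, the predictor. It does not say whose viral load will be missing.

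Which adherence measure is the predictor, and how days after withdrawal are counted, are separate questions of missing detail. This point does not rest on them.

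**Conclusion.** The concern holds as a minor one. Missing-as-detectable is not reliably conservative in this model. Under the assumed inputs, a true odds ratio of 2.33 could be reported as anything from 0.77 to 3.05, depending on suppression rate and on where the missingness falls. The condition is that some participants with missing values are truly suppressed, which the D.2 entry criteria allow but do not establish. The documents give neither the suppression rate in this sample nor the relation of missingness to adherence, so the direction and size of any bias in this trial cannot be stated.

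The scope is one secondary association model. Suppression on adherence is not among the secondary outcomes listed under Study Design (healthcare access, technology acceptance, technology use). The primary GLMM and the comparisons between arms do not use this rule as written.

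**What to change.** Keep the missing-as-detectable fit and pre-specify one of the following beside it:

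- a fit to observed viral loads, most simply by stating in D.9 that the 'as treated' analysis covers this model; or
- multiple imputation of missing viral load using baseline and 3-month viral load and the CASE index.

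State the assumption behind each result: all missing values detectable for the first, missing at random for the second. Show both, and do not claim an association, or its size, that appears under only one of them.

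The cost is a few sentences in D.9 and one extra model fit, plus a small imputation step if that route is chosen. The drawback is that the observed-data or imputed result is itself biased if missing values are mostly detectable. For that reason neither analysis should be declared the correct one.

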the end of the trial). If the adherence rate for the control group increases 4%, from 80% to 84% at the end of the trial, we will have 88.6% power to detect a 5% difference in adherence between the intervention and control group. In this case, the intervention group's adherence rate increased an additional 5% (or $4\% + 5\% = 9\%$) from 80% to 89% at the end of the trial.

D.5. Baseline Screening and Assessment.

Potential study participants will complete a phone screening that assesses eligibility. If eligible, participants will attend a baseline session described below.

D.6. Randomization.

Study participants will be randomized (1:1) to Wise App intervention or control arm. We will use a variable permuted randomized block design⁶⁸ where the block size itself is randomly selected (i.e., blocks of four to eight). The advantage of the permuted block design is that treatment assignment is pre-determined before the trial begins and then assignment remains static throughout the course of the trial⁶⁹. Participants will be randomized based on the use of computer-generated random numbers at baseline. The randomization database will be stored on a password protected computer at Columbia University and will only be accessible to [name].

D.7. Procedures.

Upon enrollment in the study, participants will come to the study site, Columbia University School of Nursing to complete consent forms. Following informed consent, study participants will complete a number of baseline questionnaires including socio-demographic characteristics, physical health measurements, behavioral data, health status and social desirability (See Table 3)⁷⁰. Survey instruments will be collected through Qualtrics, a secure, Web-based application designed to support data capture for research studies, providing an intuitive interface, audit trails, and automated export. Qualtrics is a free service offered through Columbia University Medical Center.

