Following the completion of the baseline study instruments, study participants in both arms will be given a CleverCap™ Lite dispenser and trained on how to use it, as well as a fitness tracker that will be synced to Wise App. Study participants in both arms will be trained by study team members on how to use the different features of the Wise App. Those in the intervention group will receive medication reminders while those in the control group will receive reminders about completing their step goal. Participants in both arms will be given a document that includes contact information for the project team, information about compensation, study reminders, and will also receive a telephone call from a research assistant 1 week after enrollment to assist with any technical problems with the app or the CleverCap™ Lite dispenser and biweekly thereafter.

Participants will be texted appointment reminders for study visits via Qualtrics. Hard to reach participants will also be sent scheduling reminders through the Qualtrics system and encrypted e-mails from the study's secure CUMC e-mail address.

Token of appreciation: Participants will be given \$40 at the baseline visit, \$50 + up to an extra \$25 for app challenges completed at the 3 month visit, and \$60 + up to an extra \$25 for app challenges completed at the 6 month visit (up to a total of \$200 for participation) and for providing a blood sample (or recent lab results) for viral load/ CD4 testing and completion of study questionnaires. Participants will also have the option to have the cost of their transportation to and from the study site paid for, through a ridesharing service.

D.8. Operationalization of Outcome Measures.

The primary outcome will be ART adherence, measured by the CleverCap™ dispenser. The CleverCap™ dispenser will automatically record each time a participant opens the dispenser. We will collect adherence data each day from the start to the end of trial (day 1 to 6 months), and it is a count response (number of times taking medication each day). Frequency of app use will be counted each time a participant opens the app.

Table 3. Study Measures

Tool		Measurement Time Points
Demographic Variables and Potential Confounders		
Socio-demographic characteristics	Gender, age, education, income, employment, health insurance, housing	Baseline
Behavioral Data	Use of condoms, tobacco, alcohol, substance use	Baseline, 3 and 6 months

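### The adherence–suppression model judges confounding on a relation that it does not estimate, so the check says nothing about its own odds ratio

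*Combined protocol and SAP*

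**What the plan says.** Section D.9 ends its list of secondary analyses with this: "we will assess the relationship between adherence (independent variable) and virologic suppression (dependent variable) using GLMM logistic regression", with missing viral load counted as detectable. On covariates it commits: "This model will include personal level factors as covariates so we can test for potential confounding by covariates (i.e., age, gender, and health literacy"). Confounding is then to be judged by "inspecting for changes in the point estimate of the relation between study group and adherence".

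The same closing words end the paragraph on the primary model. There, adherence is the outcome, the model contains the group indicator INT, and its coefficient β2 "is the difference in change in adherence rate between the intervention group and the control group".

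On timing, section D.7 (Procedures) states: "Following the completion of the baseline study instruments, study participants in both arms will be given a CleverCap" dispenser. Table 3 schedules viral load and the self-reported CASE Adherence Index at baseline, 3 and 6 months, and the dispenser daily. Section D.9 does not say which adherence measure, or which viral load samples, enter the adherence–suppression model.

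**The concern.** Study group is allocated at random (section D.6: "Study participants will be randomized (1:1) to Wise App intervention or control arm"). Adherence is not. Among the analyses of adherence and virology, this one is therefore observational, and it most needs a working check for confounding. The check written for it looks at a different relation, one whose expected value randomisation protects against baseline confounders.

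Section D.8 says that further measures, viral load among them, serve to validate what the dispenser records. If dispenser adherence is the exposure here, an odds ratio inflated by a shared cause of good adherence and suppression would overstate how well the primary-outcome device tracks virology, and the stated rule would give no reliable warning.

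**Working it through.** **1. The two models side by side (section D.9).**

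| | Primary model | Adherence–suppression model |
|---|---|---|
| Outcome | Adherence (daily dispenser openings) | Virologic suppression |
| Exposure of interest | Study group, by time | Adherence |
| Study-group term | Yes (INT) | None given |
| Exposure randomised | Yes | No |
| Relation inspected for confounding | Study group to adherence | Study group to adherence |

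The last row fits the first model only. Adding a study-group term to the second would not rescue it: its coefficient would be study group to suppression given adherence, not study group to adherence. No other section gives a confounding check for the adherence–suppression estimate.

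**2. Inputs for an illustration.** The plan gives no figure for this analysis, so there is none to reproduce. From the documents: 1:1 allocation; section D.4, "We will recruit 200 individuals", with 25% attrition, so 200 × (1 − 0.25) = 150. Assumed, not in the documents: mean adherence about 75%, an arm effect of 0.43 logits, a true odds ratio of 1.35 per 10 adherence points, and one standardised baseline factor c acting with strength k on the logit of both adherence and suppression.

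- Adherence: A = expit(logit 0.75 + 0.43·arm + k·c + e), with e ~ N(0, 1)
- Suppression: P = expit(−2 + 0.3·(10A) + k·c), so the true odds ratio is exp(0.3) = 1.35

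**3. Large-sample result (N = 200,000).**

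| k | Odds ratio without c | Odds ratio with c | Log odds ratio without c, relative to 0.3 | Shift in arm-to-adherence estimate (about 6.5 points) |
|---|---|---|---|---|
| 0.5 | 1.49 | 1.35–1.36 | ln 1.49 / 0.3 = 1.33 | 0.02 points |
| 0.7 | 1.58 | 1.35–1.36 | ln 1.58 / 0.3 = 1.52 | 0.02 points |
| 1.0 | 1.73 | 1.35–1.36 | ln 1.73 / 0.3 = 1.83 | 0.09 points |

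On average, the inspected estimate does not respond to confounding of the odds ratio. Odds ratios can also change on adjustment without confounding, but that effect pulls the unadjusted value towards 1, so it does not explain these increases.

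**4. One trial of the planned size (N = 150).** The shift in the arm-to-adherence estimate on adjusting for c averages about zero. Within a single trial, its standard deviation is 1.3 to 2.4 points over the three values of k, and it exceeds 10% of the estimate in 58–80% of trials (10% is an assumed threshold; the plan gives none). These movements are chance imbalance in c between arms. Their correlation with the actual confounding of the odds ratio is at most 0.09 in size.

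**5. Second set of assumptions.** Adherence near 80% with an arm effect of about 6 points (the section D.4 example), 180 binomial daily doses and an assumed true odds ratio of 1.5:

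| Strength per SD | Odds ratio without factor | With factor | Inflation of log odds ratio | Arm-to-adherence, without / with (points) |
|---|---|---|---|---|
| 0 | 1.50 | 1.50 | 0% | 6.36 / 6.36 |
| 0.3 | 1.59 | 1.50 | 16% | 6.40 / 6.42 |
| 0.5 | 1.73 | 1.50 | 35% | 6.34 / 6.37 |
| 0.8 | 1.97 | 1.51 | 64% | 6.26 / 6.29 |

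The pattern is the same.

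**The case against.** The strongest reply is that one phrase has been carried over from the primary-model paragraph, in the last-listed secondary analysis, and little follows from it. Several parts of that reply stand.

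- **A reader might infer that the odds ratio will be reported unadjusted.** The text does not support this. The primary model may include covariates; this one is to include them. For age, gender and health literacy the planned odds ratio is already adjusted, and in the simulations the model containing the confounder recovers the true value. The inflated figures apply only to a factor left out.
- **A reader might infer that the check will almost always report no confounding.** Step 4 shows otherwise at this sample size. The inspected estimate often moves by a noticeable amount, but for reasons unrelated to confounding of the odds ratio. The check can miss real confounding or raise a false alarm.
- **A reader might infer that baseline viral load enters as a response with no exposure to pair with it.** Section D.9 specifies neither dispenser adherence nor which viral loads are used, and the CASE index supplies a baseline adherence value. The timing problem arises only if dispenser adherence is the exposure. Nor do the documents show that baseline viral load is the strongest predictor of later suppression.
- **Inspecting the right coefficient reveals nothing about a factor that is never entered.** This is correct, and is why the covariate list has to be addressed together with the wording.

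What the reply does not remove is that the rule as written cannot be carried out on the model to which it is attached.

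**Conclusion.** The point holds in this form: the stated check names a relation that the adherence–suppression model does not estimate, and it carries no information about confounding of the relation that the model does estimate. This follows from the text and needs no simulation.

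The size is illustrative. With a factor of moderate to strong effect on both adherence and suppression left out, an odds ratio of 1.35 per 10 adherence points becomes about 1.5–1.7. The strength of the factor, the true odds ratio and the adherence level are assumptions, and the simulations ignore repeated measures and the rule that counts missing viral load as detectable. The exposure is limited to factors outside the three named covariates, such as baseline viral load and substance use, both of which are collected. The primary comparison is unaffected. The plan should be corrected, but the matter is confined to one secondary analysis.

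**What to change.** Replace the closing sentence of the adherence–suppression paragraph in section D.9 with:

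> The adherence-suppression odds ratio will be reported unadjusted and adjusted for age, gender, health literacy, study group and baseline viral load; confounding will be judged by the change in the adherence-suppression odds ratio.

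If the team regards other collected factors, such as substance use, as confounders, name them in the same sentence.

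State which adherence measure is the exposure. Where it is dispenser adherence, use the month-3 and month-6 viral loads as responses, each paired with dispenser adherence before the date of that sample, because the dispenser is issued only at the baseline visit. The sample date matters because section D.8 lets participants supply recent laboratory results instead of a study blood draw. Enter baseline viral load as a covariate.

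The cost is a change of wording; every variable is already collected. The small downside is that baseline viral load is not used as a response in the dispenser-based model.
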